- c* At the end of screening, investigators will determine the eligibility of the screened patients for participation. The randomization IRT call will be made at the Visit 2- Step 1. Patients will be informed by the study sites of their randomization group and Visit 2- Step 2 will be scheduled for the baseline assessments within 1 week (+/- 4 days).
Glucose meters with Bluetooth access and associated accessories (lancet, control solutions, test strips, etc), e-diaries features, and instructions will be shipped to all eligible patients. Patients will use the study provided glucose meters throughout the study.
- d* Physical examination will be performed at the in-person visit in the traditional group. In the virtual group, physical examination will be performed on-site, in-person, between randomization IRT call and the first IMP administration. All other assessments will occur remotely on the day of the first IMP administration (Day 1).
- e* Only for patients randomized in virtual group:
- They will receive the Bluetooth devices for their remote participation and the IMP (Toujeo®) before Visit 2-Step 2.
 - Shortly after randomization (IRT call), they will be scheduled for an in-person visit to allow for the initiation physical examination performed by the investigator.
 - They will be further trained on the Bluetooth devices utilization.
 - The IMP starting date and dose will be instructed by the investigator at the time of Visit 2-Step 2. The first IMP (Day 1) data will be documented with the dose in the e-CRF.
 - All study assessments, including vital signs and weight, will be done via the Bluetooth devices by the patients at home.
 - Patients located in the United States (US) will receive a laboratory requisition and have their blood drawn at any local Quest®. For patients located in Canada, blood draw will be performed by the Homecare via The MRN.
 - Unscheduled on-site visits or Homecare physician visits (depending on the patient's location) only for safety assessment could be scheduled as deemed necessary by the investigator (ie, performance of physical examinations is critical to determine a diagnosis or further evaluation procedure for an AE).
- f* IMP dose will be titrated at the investigator's discretion to achieve the fasting glycemic target while avoiding hypoglycemia

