8.3 BLINDING PROCEDURES

There will be no blinding procedures during the present study. All patients will self-inject themselves Toujeo (open label way) during the trial.

The study conduct approach (virtual or traditional) cannot be blinded to physicians or patients. As virtual and traditional approaches are distinguishable in terms of database source, it is also not possible to blind this information to the Data Management team.

Despite the open-label nature of study, assessment of outcomes will be based on objectively collected data, ie, assessments of HbA1c and FPG by central laboratories blinded to patients' study approach group. Also, the sponsor team will be provided blinded summary tables and listings to follow the study before database lock.

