10.1.2.2 Visit 2-Step 2 (Week 0)

This is the baseline visit (onsite visit for the traditional group and mixed onsite-virtual visit for the virtual group). The full list of assessments is provided in the study flow chart ([Section 1.2](#)). Additional details are provided below for a number of assessments.

For the traditional group:

- During the week prior to the scheduled site visit:
 - patients should perform at least one day of 7-point SMPG
 - The baseline questionnaires (DTSQs, DDS, HFS, WPAI-SP, OSEP part 1, RUQ, and OSES part 1 resource requirements) should be administered by patient via parallel 6 portal
- Patients will bring the glucose meter to the site and SMPG data will be collected.

- Any AE/SAE, including hypoglycemia, that occurred since Visit 1 will be documented.
- A disease-focused initial physical examination will be performed by the investigators at the study site, including neck palpation of thyroid, screening for diabetic neuropathy (eg, assessment of appearance of feet and ankles, reflexes, and vibration perception at the great toes) and a check for injection site reactions.
- The IMP, Toujeo basal insulin, will be dispensed. The first dose of IMP may start on the day of this visit (ie, evening dosing) or the second day (ie, morning dosing). Patients will document the dose and date/time in the eDiary.

For the virtual group:

- Patients will receive the Bluetooth devices by mail and IMP by DTP before Visit 2-Step 2. Upon receipt, they will activate the devices (Bluetooth, e-diary, digital BP and pulse device, etc) and confirm to the study site the successful connection with the virtual platform.
- They will be scheduled within a week to visit study site in-person for the investigator to perform the physical examination. No other assessments will be done at this onsite visit.
- Patients will be guided for using the device to measure BP, heart rate, and weight appropriately.
- The 7-point SMPG will be performed for at least 1 day within the week prior to the first dose of the IMP and the data will be immediately available via the Bluetooth for investigator's review.
- Any AE/SAE, including hypoglycemia, that occurred since Visit 1 will be documented in the eDiary.
- Baseline PROs should be completed electronically independently from influence of the investigator and the site staff.

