11.4.3.2.1 Analysis of diabetes control PROs

For each questionnaire a descriptive summary at each applicable visit (baseline and/or Week 24) and change from baseline to Week 24 will be provided, including:

- DTSQs and DTSQc subscale scores (total treatment satisfaction, perceived frequency of hyperglycemia, and perceived frequency of hypoglycemia, see [Section 9.2.2.1](#))
- HFS-II total score and subscale scores (HFS-B and HFS-W)
- DDS: total score, subscales scores, distress category for total and subscales ([Section 9.2.2.1](#))

The change in DTSQs, HFS-II, and DDS scores from baseline to Week 24 will be analyzed using an ANCOVA. This model will include fixed categorical effects of approach group, on randomization strata of screening HbA1c (<7.6%, ≥7.6%) and randomization strata of sites as well as continuous fixed covariates of corresponding baseline score.

Average scores at Week 24 in total treatment satisfaction score, hyperglycemia perception, and hypoglycemia perception score from DTSQc will be analyzed using an ANCOVA model. This model will include fixed categorical effects of approach group, on randomization strata of screening HbA1c (<7.6%, ≥7.6%) and randomization strata of sites as well as continuous fixed covariates of corresponding baseline score from DTSQs.

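### Baseline questionnaires are completed after patients have been told their group, so change scores and ANCOVA covariates may carry a reaction to allocation

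*Protocol*

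**What the plan says.** **Order of events.** Protocol 1.2 (flow chart, footnote c) puts randomization first: "The randomization IRT call will be made at the Visit 2- Step 1". Disclosure follows: "Patients will be informed by the study sites of their randomization group and Visit 2- Step 2 will be scheduled for the baseline assessments". Protocol 8.1.5 sets Visit 2-Step 2 at 7 (± 4) days after the call. The flow chart marks DTSQs, DDS, HFS-II, WPAI-SP, OSEP part 1 and RUQ for the first time at Visit 2-Step 2; none of them is scheduled earlier.

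**Completion by group.** Protocol 10.1.2.2 says, for the traditional group in the week before the site visit: "The baseline questionnaires (DTSQs, DDS, HFS, WPAI-SP, OSEP part 1, RUQ, and OSES part 1 resource requirements) should be administered by patient", using the study portal. (OSES part 1 in that list is completed by the investigator according to Protocol 9.2.3.1, and is left aside here.) For the virtual group it says: "Baseline PROs should be completed electronically independently from influence of the investigator and the site staff".

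**Blinding.** Protocol 8.3: "The study conduct approach (virtual or traditional) cannot be blinded to physicians or patients".

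**Analysis.** Protocol 11.4.3.2.1: "The change in DTSQs, HFS-II, and DDS scores from baseline to Week 24 will be analyzed using an ANCOVA", with a model that has group and strata effects "as well as continuous fixed covariates of corresponding baseline score". WPAI-SP and OSEP part 1 get the same model (Protocol 11.4.3.1.1). DTSQc at Week 24 is adjusted for baseline DTSQs. RUQ is only described, including its change from baseline. The SAP (2.4.7.2 to 2.4.7.5) keeps these analyses, and its Table 2 accepts baseline forms dated from Day -28 to Day 1.

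**Current status.** SAP section 2 reports early termination with 15 patients randomized and limits the analysis to basic descriptive statistics.

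**The concern.** Randomization balances, in expectation, what was measured or fixed before it. A score taken after the patient knows the group is a post-randomization variable, and in an open-label comparison of two ways of taking part in a trial it can respond to the assignment. Subtracting it, or adjusting for it, can then create a group difference that is not there at Week 24, or remove part of one that is.

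The exposure is not the same for every instrument. WPAI-SP asks how study participation affects work and activities (Protocol 9.2.1.2). Before completing it, a virtual patient may already have made the on-site trip for the physical examination and set up the devices, whereas a traditional patient is asked to complete it before the site visit. That difference in timing needs no psychological reaction to produce an imbalance. What is at stake is the reading of the secondary PRO changes, in a pilot meant to inform full-scale studies (Protocol 4).

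**Working it through.** **1. Schedule.** No figure in the plan depends on this point, so the first check is of order.

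| Step | When | Source |
|---|---|---|
| HbA1c and FPG baseline | Visit 1-Step 2, Week -2 | Protocol 9.1, 9.2.2.2 |
| Laboratory results received, eligibility settled | before the call | Protocol 10.1.2.1 |
| IRT randomization, group disclosed | Visit 2-Step 1, Week -1 | Protocol 1.2 footnote c |
| Devices shipped; on-site examination (virtual) | after the call | Protocol 10.1.2.1, 1.2 footnote d |
| Baseline PROs | Visit 2-Step 2, or the week before it (traditional) | Protocol 1.2, 10.1.2.2 |

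The visit falls 7 − 4 = 3 to 7 + 4 = 11 days after the call. A traditional patient may answer earlier in that interval, but the instruction applies only once the group is known, so the forms still follow disclosure. The HbA1c baseline precedes randomization.

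**2. Consequence, as algebra.** Let allocation move one group's mean baseline by d (in SD units), and let b be the within-group slope of Week 24 score on baseline.

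- Change score: bias = (Week 24 difference) − d. With no Week 24 difference this is −d.
- ANCOVA: group coefficient = (Week 24 difference) − b·d. With no Week 24 difference this is −b·d.

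The documents give neither d nor b. The ranges below are assumptions.

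| d | Change score | ANCOVA, b = 0.3 | b = 0.5 | b = 0.7 |
|---|---|---|---|---|
| 0.1 | −0.10 | −0.03 | −0.05 | −0.07 |
| 0.2 | −0.20 | −0.06 | −0.10 | −0.14 |
| 0.3 | −0.30 | −0.09 | −0.15 | −0.21 |
| 0.5 | −0.50 | −0.15 | −0.25 | −0.35 |

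A simulation of 400,000 patients at d = 0.2 gave ANCOVA coefficients of −0.060, −0.098 and −0.143, in agreement.

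**3. The opposite case.** If the reaction lasts to Week 24 at the same size, the change score shows d − d = 0 and ANCOVA shows (1 − b)·d. At d = 0.2 that is 0.14, 0.10 or 0.06 SD for b = 0.3, 0.5 or 0.7. So the direction of the error is not known in advance.

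**4. Scale.** SAP 2.5.2 calls a between-group effect size below 0.2 negligible and 0.2 to 0.5 small, and computes it from LS means. On the table above, the ANCOVA error alone passes 0.2 only at d = 0.3 with b = 0.7, and at d = 0.5 with b of 0.5 or more. With 15 patients split 7 and 8 (the split is assumed) and a baseline–follow-up correlation of 0.5, the variance of a change is 2(1 − 0.5) = 1, and the standard error of the difference in mean change is √(1/7 + 1/8) = 0.52 SD. A 0.2 SD shift is then 0.20/0.52 = 0.39 of a standard error.

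**The case against.** - **Exposure is not bias.** A reader might infer that every PRO comparison is biased. The documents do not support that: they show that baselines follow disclosure, not that patients reacted or by how much. This objection stands.
- **Recall periods dampen the effect.** HFS-II looks back 3 months, DDS a month and RUQ 4 weeks (Protocol 9.2.2.1, 9.2.1.4). Taking 91, 30 and 28 days, 11 days after disclosure is at most 12%, 37% and 39% of the period. DTSQs covers the past few weeks. DTSQs, DDS and HFS-II concern diabetes and its treatment, and the study insulin is the same in both groups and not yet started. This stands for those three; it does not help WPAI-SP, whose subject is participation itself.
- **Completion is shielded from site staff.** The provision is listed for the virtual group and limits staff influence. It does not hide the allocation, so it does not answer the point.
- **The analysis is now descriptive.** With 15 randomized, the ANCOVA consequence is largely moot and sampling noise dominates. This stands. Descriptive changes still use these baselines, however, and an unadjusted change carries the whole shift.
- **Imbalance would be visible.** The plan already summarizes baseline and Week 24 scores by group for most of these instruments. That helps a reader but does not separate chance imbalance from a reaction.
- **Feasibility.** SAP 2.5.4 has PROs arriving from the e-diary, whose features ship after the call. But Protocol 10.1.2.2 names the Parallel 6 portal for the traditional group's baseline questionnaires, and flow-chart footnote a shows that patients already use it for eConsent.

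**Conclusion.** The point holds as a cheap improvement to the design. The baseline scores of the DTSQs, DDS, HFS-II, WPAI-SP and OSEP part 1, the DTSQc covariate and the descriptive RUQ change may carry a reaction to allocation, because each baseline follows disclosure in an unblinded trial. The size is unknown; the figures of 0.1 to 0.5 SD (change scores) and 0.03 to 0.35 SD (ANCOVA) rest wholly on assumed shifts and slopes and on no Week 24 counterpart.

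A reader might also infer that the primary result or all satisfaction and burden outcomes are compromised. They are not: HbA1c is drawn at screening, and WIWI and OSEP part 2 are collected only at Week 24 and analyzed without a baseline covariate.

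**What to change.** **Design, and any full-scale study that reuses it.** Send the DTSQs, DDS, HFS-II, WPAI-SP, OSEP part 1 and RUQ through the study portal once eligibility is confirmed, and require completion before the Visit 2-Step 1 IRT call. Only eligible patients are asked, so screen failures carry no burden. In Table 2 of the SAP, end the baseline window for these PROs at the patient's randomization date and time instead of Day 1; a fixed study day will not do, because the interval to first dose varies. The table should also list OSEP part 1, since its first block lists OSES part 1, which has its own block. Reconcile flow-chart footnote o (traditional group answers at the site, yet before visiting it) with Protocol 10.1.2.2 (portal, in the week before).

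**Report on the 15 patients.** State that baseline PROs followed disclosure of group, and show baseline and Week 24 scores by group beside the changes, for every affected instrument.

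**Cost.** A change to the flow chart and a portal setting. Baseline moves about one week further from first dose, and a patient slow to answer may be randomized a little later. The report needs one sentence and a table layout that is mostly planned already.

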3 LIST OF ABBREVIATIONS

ADA:	American Diabetes Association
AE:	adverse event
AESI:	adverse event of special interest
ALT:	alanine transaminase
ANCOVA:	analysis of covariance
ANOVA:	analysis of variance
BP:	blood pressure
CI:	confidence interval
CPMP:	Committee for Proprietary Medicinal Products
CRF:	case report form
CV:	curriculum vitae
CVD:	cardiovascular disease
DDS:	Diabetes Distress Scale
DRF:	discrepancy resolution form
DTP:	direct to patient
DTSQ:	diabetes treatment satisfaction questionnaire
DTSQc:	Diabetes Treatment Satisfaction Questionnaire change
DTSQs:	Diabetes Treatment Satisfaction Questionnaire status
ECG:	electrocardiogram
e-CRF:	electronic case report form
EOT:	end of treatment
FPG:	fasting plasma glucose
GCP:	good clinical practice
HbA1c:	glycated hemoglobin A1c
HFS-B:	hypoglycemia fear survey-behavior
HFS-II:	Hypoglycemia Fear Survey-II
HFS-W:	hypoglycemia fear survey-worry
HLGT:	high level group term
HLT:	high level term
ICH:	International Conference on Harmonisation
IEC:	independent ethics committee
IMP:	investigational medicinal product
IRB:	institutional review board
IRT:	interactive response technology
ITT:	intent to treat
MedDRA:	medical dictionary for regulatory activities
MMRM:	mixed effect model with repeated measures
MRN:	Medical Research Network
NIMP:	noninvestigational medicinal product
NPH:	neutral protamine Hagedorn
OSEP:	overall study experience-participation

OSES:	overall study experience-sites
PCSA:	potentially clinically significant abnormality
PRE:	pen-related event
PRO:	patient reported outcome
PT:	preferred term
PTC:	product technical complaint
RUQ:	resource use questionnaire
SAE:	serious adverse event
SC:	subcutaneous
SD:	standard deviation
SMBG:	self-monitoring of blood glucose
SMPG:	self-monitoring of plasma glucose
SOC:	system organ class
SUSAR:	suspected unexpected serious adverse reaction
T1DM:	Type 1 diabetes mellitus
TEAE:	treatment-emergent adverse event
ULN:	upper limit normal
US:	United States
USPI:	United States package insert
WIWI:	was it worth it
WOCBP:	woman of child-bearing potential
WPAI:	work productivity and impairment, work productivity and impairment-study participation
WPAI-SHP:	WPAI-specific health problem
WPAI-SP:	Work Productivity and Impairment-study participation

4 INTRODUCTION AND RATIONALE

Across the clinical landscape, there are an increasing number of clinical studies with increased study complexity. These traditional studies typically have several factors which contribute to recruitment and retention challenges, as well as reduced patient engagement, study compliance, and, ultimately, data quality issues. Common factors include the requirement for a patient to stay near the clinical site, affiliation with a physician in a pharmaceutical investigator network, ability to schedule life events around specific study requirements, or have medical insurance.

Traditional, complex studies increase patient burden with the often rigid study requirements. Additional frustration can occur when a patient does not receive their individual or study results. In addition, the increased study complexity and operational processes by many of the study sponsors place an additional burden on the clinical sites and increase the operational costs (1), which is a main driver of total study cost.

The strategic use of innovative methods and mobile health technologies in clinical studies may provide a true patient-centric operational model, improving both patient experience and study compliance. This innovative approach could facilitate patient participation beyond the established sponsor-investigator network, by allowing for recruitment of geographically remote patients. For the clinical site, this approach may provide processes equivalent with the current clinical practice, while allowing sites to be more efficient in the execution of clinical studies. These benefits extend to the sponsor: by eliminating geographical restrictions, a smaller number of sites may be needed per trial – thereby reducing monitoring efforts and saving costs.

With the impact of increasing smartphone use, decreasing age and socioeconomic barriers due to technology (2), and the increasing number of patients seeking disease specific online communities (3), creating an operational approach aligned with these trends can allow for a simple, cost effective, and more encompassing clinical trial approach.

The first industry sponsored virtual study was a Phase IV overactive bladder study in the United States (US), conducted by Pfizer in 2011. The study did not reach a successful conclusion, but there were many lessons learned (3). These lessons learned shared by Pfizer and the experiences gained from vendors who participated in the virtual study have benefited the larger pharma community. The integration of mobile health technology, telemedicine, and remote sensors into classic clinical studies has increased significantly over the past decade (4). Pfizer's first attempt at the virtual study was an evolution of this continued innovative clinical activity. Sanofi eStudy will be a compilation of collective experience and lessons learned to provide the best chance of success.

Diabetes (type 1 and type 2) affects 415 million people globally, approximately 22 million adults and 0.54 million children have Type 1 diabetes (5). The effect of type 1 diabetes-related complications on patients and healthcare systems is significant, with reported incidences of proliferative retinopathy, nephropathy and cardiovascular disease of 47%, 17% and 14%, respectively, after 30 years of diabetes (6). There are a number of barriers to glycemic control in type 1 diabetes, including the occurrence and fear of hypoglycemia and the complexity and

demands of day-to-day management, in particular the need for frequent self-monitoring of blood glucose (SMBG) and regular adjustments in insulin dosing. These challenges have an enormous impact on patient quality of life and healthcare cost (7, 8). Utilizing mobile health technologies (eg, assisting in medication compliance, SMBG monitoring, reinforcing diabetes health, etc) could play an important role in reducing some of the common barriers, improving glycemic control, and increasing empowerment of the patients by supporting them in informed decision making.

MSC15146 (eStudy) is a pilot clinical study to evaluate the methodology of a virtual clinical trial conduct in patients with type 1 diabetes prior to performance of full-scale studies. The effect of the virtual versus traditional trial conduct on multiple outcomes including study activities, investigational medicinal product (IMP)/noninvestigational medicinal product (NIMP) compliance, patient retention, etc, will be analyzed to assess the usability and appropriateness of the virtual methodology. The virtual study conduct on glycemic control will be evaluated by the changes in glycated hemoglobin A1c (HbA1c), fasting plasma glucose (FPG), and self-monitoring of plasma glucose (SMPG) profile in the two groups that will receive the same basal plus insulin regimen during the study period. In addition to the glycemic parameters, the study introduced a number of patient reported outcomes (PROs), including the diabetes related questionnaires that assess glycemic control, fear of hypoglycemia, satisfaction of treatment from patients' perspective, and other questionnaires that assess the operational process, physician-patient relationship, trial time consumption, burdens to trial patients, etc.

For the first time in a Sanofi study, designated data (eg, SMPG, safety and central lab results, etc) will be available to patients in the virtual group, using a smartphone. This direct access to their data could support patients in diabetes management by helping them make better-informed decisions, which may have a positive impact on metabolic outcomes.

With the above study design the eStudy outcomes are expected to provide useful information for the future use of a virtual approach about the feasibility and appropriateness in both glycemic control and operational process, such as IMP adherence, barriers, burden to patients and sites, study complexity, patient compliance, data quality etc.

